#### 9.1.1.1 Evaluation of Biomarkers

Samples for biomarker assessments will be obtained in blood/urine and stored (frozen) for future analysis for subjects who consent to have their leftover samples retained.

#### 9.1.2 Physical Examinations

Physical examinations will be performed in accordance with the [Schedule of Events](#).

The physical examination will include a review of FSGS-related manifestations which will also be recorded. A complete physical examination will be conducted at the initial screening assessment, and an abbreviated physical will be performed at all other visits as per the [Schedule of Events](#). The abbreviated examination will consist of checking the normality or abnormality of the following body systems: general appearance, cardiovascular system, and pulmonary system. Any abnormalities will be recorded in the eCRF and reported as an AE. Because the investigational medication is an immunosuppressant, physical examination will include clinical examination for tumors.

### 9.1.3 Vital Signs

The following vital signs will be measured in accordance with the [Schedule of Events](#):

- Resting BP (systolic and diastolic)
- Resting heart rate (HR)
- Body temperature (°C or °F)
- Weight (kg)
- Height (cm)

To avoid variability, the same method of obtaining body temperature should be used throughout the study.

At stability assessments, BP only will be included.

Height will be recorded at the initial screening assessment only.

#### 9.1.3.1 Blood Pressure Management

Blood pressure and HR will be measured with the subject in a sitting position after 5 minutes of rest. The procedure for standardized measurement of BP is detailed in [Appendix 2](#).

If the mean BP measure is  $>130/80$  mmHg (determined by the mean of the second and third repeats of 3 readings), the subject's BP will be managed per local practice. If the BP remains uncontrolled with the maximal doses of first- and second-line antihypertensive therapies referenced in [Appendix 1](#), then the Investigator should contact the Medical Monitor to consider dose adjustment of the study treatment. See [Section 7.7, Increased Blood Pressure](#) for management of increased BP.

### 9.1.4 Standard 12-lead Electrocardiogram

The electrocardiogram (ECG) will be a standard 12-lead tracing performed at the investigational site, assessed by a qualified physician at the investigational site, and retained as a source document. Any abnormalities will be recorded in the eCRF. Electrocardiograms will be recorded after the subject has been in a resting, supine position for at least 5 minutes. Abnormal ECG tracings can be reviewed by the Medical Monitor. Significant abnormalities, including findings that may prompt discontinuation of study treatment, must be discussed with the Medical Monitor.

Electrocardiograms will be measured at the initial screening assessment, Day 1, and Week 24.

#### **9.1.4.1 Procedures to Manage a Treatment-Emergent Increase in QTcF**

In the event that a subject has a corrected QT interval duration corrected for heart rate using method of Fridericia (QTcF) value exceeding 500 msec, or an increase >60 msec from baseline, the Medical Monitor must be informed. The subject will be asked to return for an unscheduled visit within 24 hours and the ECG will be repeated (confirmed), in triplicate (i.e., three 10-second ECGs in rapid succession within 1 minute). If the repeat measurements confirm that the QTcF is >500 msec or >60 msec from baseline, study treatment will be discontinued and the subject followed until the QTcF value either returns to baseline or until, in the judgment of the Investigator, further evaluation is not clinically indicated.

If study treatment is discontinued, the subject should continue in the study for all remaining scheduled study visits.

#### **9.1.5 QoL Assessments**

Assessments for QoL will be conducted at Day 1, Week 24, Week 25 and Week 26.

The PROMIS assesses physical function, pain interference, and fatigue. See [Appendix 7](#).

The KDQOL-SFTM survey is a kidney disease-specific measure of QoL that assesses general health, kidney disease and its effects on daily life, and satisfaction with care. See [Appendix 8](#).

#### **9.1.6 Voclosporin Pharmacokinetic and Biomarker Assessment**

Blood samples for PK assessments will be taken at Week 4 and Week 24. PK samples will be drawn prior to study treatment dosing (trough sample), and at 1, 2 and 4 hours post-dose. These samples will be analyzed for voclosporin. Should a subject experience a serious adverse event (SAE), require a dose modification or be withdrawn from treatment, a blood PK sample will be taken (with a trough sample preferred) for later determination of drug level. If a subject has discontinued from study treatment, further PK samples are not required.

Blood and urine samples for biomarker assessments will be taken at Day 1, Week 4 and Week 24, samples will be collected prior to study treatment dosing.

### **9.2 Schedule of Assessments**

A detailed schedule of assessments (including all protocol-required assessments, visits, and visit windows) is located on the [Schedule of Events](#). No study-related assessments will be performed (including changes to current medications to meet study eligibility) until the subject has provided signed and dated informed consent. Every effort will be made to keep the subject within the requested visit schedule. If a subject is seen outside of the visit window listed on the [Schedule of Events](#), the reason must be clearly documented in the source notes. The Investigator (or designee) should contact Aurinia for assistance with getting the subject's

schedule back on track in order to avoid large variances in treatment exposure or to avoid delaying overall study timelines.

### **9.2.1 Screening Visit and Stability Assessment Procedures**

The duration of the screening period will be approximately 4 weeks to 10 weeks (allowing for visit windows) and will consist of an initial screening assessment and 2 to 4 stability assessments to ensure that subjects meet eligibility criteria.

The initial screening assessment will include provision of informed consent; complete physical examination; medical history (including FSGS history); vital signs measurements, including weight and height; 12-lead ECG; blood and urine sample collection for central laboratory assessments, urinalysis, and urine microscopy; FMV urine collection (for determination of UPCR); a serum pregnancy test (for women of childbearing potential); and review of prior and concomitant medications and entry criteria. Following these assessments and if clinically indicated, subjects receiving steroids may start reducing their steroid dose as described in the corticosteroid dosing guidelines (see [Section 7.1.2.2, Corticosteroids](#)). Any AEs which occur after informed consent will be recorded.

Stability assessments will occur at 14-day intervals ( $\pm 3$  days) with the first assessment approximately 2 weeks after the initial screening assessment visit. Stability assessments 1 and 2 are mandatory; assessments 3 and 4 are optional if additional time is required for the subject's clinical status to stabilize. These stability assessment visits will include BP determination; blood sample collection for central laboratory assessments; FMV urine collection (for determination of UPCR); a serum pregnancy test (for women of childbearing potential); review of any AEs; and review of concomitant medications and entry criteria.

These renal disease stability assessments will be evaluated to ensure eligibility with respect to entry criteria for UPCR and eGFR.

Note that the laboratory assessments and FMV results of the last stability assessment will be used as the qualifying values for eligibility.

FMV urine samples (for determination of UPCR) will be collected at all visits during the screening period and must be returned and the results evaluated prior to Baseline/Day 1. If the FMV is for some reason not available at Day 1, Week 12 or Week 24, standard urinalysis from a 24-hour urine collection may be substituted as an exception but only after agreement is reached with the Medical Monitor.

Blood samples will be drawn according to [Table 1](#).

If the subject is from an area where TB is endemic or whose history suggests an increased personal risk, e.g., from contact with people with TB or travel to areas with endemic TB, the subject will be carefully evaluated for latent or active TB.

Women of childbearing potential must have a negative serum pregnancy test result before baseline.

If a subject has not met the requirements in Inclusion Criteria #3 due to not having renal biopsy result within the required time frame, a renal biopsy can be performed as per local procedures, after signing the study consent, provided the results can be obtained and reviewed prior to baseline.

### **9.2.2 Treatment Procedures**

Only subjects who meet all of the inclusion and none of the exclusion criteria will be eligible for study treatment.

Study medication will be dispensed per the [Schedule of Events](#), beginning on Day 1. Subjects will take their first dose of study medication on Day 2. Women of childbearing potential must have a negative serum pregnancy test during Screening and a negative urine pregnancy test result on Day 1 prior to dispensing of study treatment.

Subjects in Cohort 1, will be contacted by telephone at the end of Week 1 as a reminder to increase their dose to 2 capsules (15.8 mg) BID for 1 week, starting at Week 2. Subjects will be contacted again by telephone at the end of Week 2 as a reminder to increase their dose to 3 capsules (23.7 mg) BID, starting at Week 3, for the remainder of the treatment period (see [Section 7.1.2.1, Voclosporin](#)).

Subjects in Cohort 2, will also be contacted by telephone at the end of each week, as required up to the end of Week 3, as a reminder to increase their dose of study medication to the maximum dose selected for the second cohort.

Subjects will complete all assessments per the [Schedule of Events](#) at Day 1 and at Weeks 2, 4, 8, 12 and 18.

Adverse events and concomitant medication will be recorded prior to the conduct of other study assessments at each visit.

Assessments at visits during the treatment period include:

- PROMIS and KDQOL-SFTM QoL questionnaires will be answered by the subject, as first study procedure, at Day 1/Baseline.
- Abbreviated physical examination at Day 1.
- Vital signs including weight.
- Standard 12-lead ECG at Day 1.

- Blood and urine sample collection for analysis at central laboratory.
- FMV urine sample collection.
- Urine pregnancy testing at Day 1 (before dispensing study treatment)
- AEs.
- Concomitant medication.
- Returned capsule count and drug accountability (except Day 1).

### **9.2.3 End of Study (or Early Termination) Procedures**

On completion of treatment at Week 24 or earlier if subject is withdrawn, all assessments for Visit 8 (End of Study/Early Termination) will be completed per the [Schedule of Events](#). See also [Section 5.5, Withdrawal of Subjects](#), for further information on withdrawal procedures and criteria.

The following assessments for the end of study visit will be performed:

- PROMIS and KDQOL-SF™ QoL
- Abbreviated physical examination
- Vital signs including weight
- Standard 12-lead ECG
- Blood and urine sample collection for analysis at central laboratory
- FMV urine sample collection
- Serum pregnancy testing
- Pharmacokinetic and biomarker sampling
- AEs
- Concomitant medication
- Returned capsule count and drug accountability
- Repeat renal biopsy may be performed on a subset of patients

- Confirmation of completion/discontinuation

#### **9.2.4 Follow-up Procedures**

All subjects who complete the study or withdraw before Week 24 will be followed up at 1 week ( $\pm 3$  days) and 2 weeks ( $\pm 3$  days) after their last study treatment dose to collect any new AEs and concomitant medications. These 2 visits (Visit 9 and Visit 10) will be conducted as in-clinic visits.

Assessments for the follow-up visit are as follows:

- PROMIS and KDQOL-SF™ QoL
- Vital signs including weight
- Blood and urine sample collection for analysis at central laboratory
- FMV urine sample collection
- Concomitant medication
- AEs
- Confirmation of completed follow-up visit

#### **9.2.5 Unscheduled Visit**

Unscheduled visits may be performed during the course of the study for safety reasons. . Only the data relevant to the purpose of the visit will be collected in the source documents and eCRF. Additionally, unscheduled visits will be registered in the electronic data capture (EDC) system.

An unscheduled visit is requested in the following cases:

- After dose reduction at any time during the study (unscheduled visit within 2 weeks)
- QTcF value exceeding 500 msec, or an increase  $>60$  msec from baseline, where the ECG will be repeated (confirmed) at an unscheduled visit within 24 hours
- Decrease in eGFR  $>30\%$  compared to baseline (unscheduled visit within 48 hours), or a decrease in eGFR  $>20-30\%$  compared to baseline (unscheduled visit within approximately 2 weeks)
- Symptomatic hypertension: Systolic BP is  $\geq 165$  mmHg or diastolic BP is  $\geq 105$  mmHg with symptoms of hypertension, see [Section 7.7, Increased Blood Pressure](#) (unscheduled visit within 48 hours)

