### 2.1 Dose Rationale

This Phase 2 study is designed to initially evaluate the treatment benefit of voclosporin 23.7 mg BID in the first cohort of up to 10 subjects. The selection of this voclosporin dose for the first cohort (see [Section 7, Study Treatments](#)) was based on the previous experience with this drug in the Phase 2 LN study (AURA-LV). In AURA-LV, subjects were administered voclosporin 23.7 mg BID, voclosporin 39.5 mg BID, or matching placebo. Low-dose voclosporin was significantly superior to placebo in the proportion of subjects achieving complete renal response at Week 24 ( $p=0.045$ ). At Week 48, complete remission rates in both the low-dose (49.4%) and high-dose (39.8%) voclosporin groups demonstrated statistically significant superiority compared to the placebo (23.9%) group, ( $p<0.001$ ,  $p=0.026$ , respectively). There was no increase in efficacy with the higher dose and no significant differences between the two voclosporin groups in achievement of renal response.

This study is also designed to evaluate a further dose level of voclosporin, this dose may be higher or lower than the initial 23.7 mg BID dosing. When the first 5-6 subjects in Cohort 1 have completed 12 weeks of treatment with voclosporin, the top line efficacy and safety data will be analyzed to determine the dose level for Cohort 2. The maximum dose possible for Cohort 2 will be 39.5 mg (5 capsules) BID. If the higher dose is selected for Cohort 2, subjects still receiving treatment in Cohort 1 may have their dose increased to 39.5 mg after Week 8 if they have not demonstrated meaningful benefit from the 23.7 mg BID dose per Investigator judgement and following discussion with the Medical Monitor. Subjects enrolled after the dose decision will receive voclosporin at 39.5 mg BID and be considered part of Cohort 2.

To minimize safety concerns, a cautious dose-escalation design starting with a minimal dose of one capsule (7.9 mg) per day will be employed for all subjects (see [Section 7.1.2, Dosing Guidelines](#)).

The protocol contains provisions for management of dose (including rules for stopping treatment with study medication) based on safety concerns in particular, BP and renal function. The safety data from the use of voclosporin in LN demonstrates that these risks are dose-related, reversible, and can be managed by dose reduction and temporary interruption.

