All subjects will return for assessment of efficacy and safety at Weeks 2, 4, 8, 12, 18, and 24. See [Schedule of Events](#), for detailed information regarding visits.

All subjects, completed or withdrawn from the study, will complete the End of Treatment/Early Termination assessments (Visit 8) at Week 24, or at the time of withdrawal, and should attend two Safety Follow-up visits at 1 and 2 weeks after completion of treatment (i.e., at Week 25 (Visit 9) and Week 26 (Visit 10)) (or 7 and 14 days, respectively, following withdrawal) to collect any new AEs and concomitant medications. At the follow-up visit, UPCR and eGFR

will be assessed as well. For subject withdrawal procedures and criteria, see [Section 5.5, Withdrawal of Subjects](#).

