#### 7.1.2 Dosing Guidelines

##### 7.1.2.1 Voclosporin

Voclosporin will be taken BID with water on an empty stomach as close to a 12-hour schedule as possible, and with a minimum of 8 hours between doses. If the subject misses a dose of study treatment by less than 4 hours from the anticipated dosing time, the missed dose will be taken immediately. The next dose will be taken at the originally scheduled time. If a missed dose of study treatment is greater than 4 hours from the expected dosing time, the subject will skip the dose and take the next dose at the originally scheduled time. The variation in dosing will be recorded in the eCRFs. The dose/doses of study treatment may be held at the discretion of the Investigator. Subjects must avoid consumption of grapefruit or grapefruit-containing juice (e.g., pomelo) for the duration of their participation in the study.

The dosing of voclosporin for Cohort 1 will be as follows:

- Week 1: 1 capsule (7.9 mg) orally (PO), BID
- Week 2: 2 capsules (15.8 mg) PO, BID

- Weeks 3 to 24: 3 capsules (23.7 mg) PO, BID

Evaluable safety and tolerability data from 12 weeks of treatment in the first 5-6 subjects from Cohort 1 are required in order to make the decision to escalate to a higher dose level for Cohort 2. The selected dose may be higher or lower than 23.7 mg BID. The maximum dose possible for Cohort 2 will be 39.5 mg (5 capsules) BID. Should this dose be selected the following dosing regimen will be followed:

- Week 1: 1 capsule (7.9 mg) PO, BID
- Week 2: 2 capsules (15.8 mg) PO, BID
- Week 3: 3 capsules (23.7 mg) PO, BID
- Weeks 4 to 24: 5 capsules (39.5 mg) PO, BID

All subjects will be contacted by telephone at the end of Week 1 and Week 2 (and Week 3, if applicable) to be reminded to increase their dose.

If the 39.5 mg dose is selected for Cohort 2, subjects still receiving treatment in Cohort 1 may have their dose increased to 39.5 mg BID after Week 8 per Investigator judgement and following discussion with the Medical Monitor.

All unused study treatment (and any empty containers) dispensed to the subject will be returned at each study visit for capsule counts to check compliance. The Investigator will count the returned study treatment, and this information will be used to assess subject compliance.

This study treatment count must be documented in the eCRF and source documentation.

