## **7.4 Voclosporin Dose Modification**

### **7.4.1 Discontinuation of Study Therapy Due to Non-response**

During the treatment period, any case where the subject experiences a worsening of proteinuria, or no improvement in proteinuria from baseline, once the highest permitted dose of study drug has been achieved, should be discussed with the Medical Monitor. Subjects may be allowed to add treatment with corticosteroids (IV or oral) while continuing with study drug, or may be discontinued from study treatment and transitioned to standard of care treatment.

If the dose level of 39.5 mg BID is determined for Cohort 2, any subject still on treatment in Cohort 1 who has completed 8 weeks of treatment and shown no meaningful improvement in proteinuria may have their dose increased to 39.5 mg BID per Investigator judgement and following discussion with the Medical Monitor.

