### **7.4.2 Deterioration in Renal Function**

Serum creatinine and eGFR utilizing the CKD-EPI formula, as reported by the central laboratory, will be used for the assessment of renal function at every visit including unscheduled visits.

It is recognized that eGFR may be unreliable at higher values ( $>100$  mL/min/1.73 m^2). FSGS subjects with nephrotic-range proteinuria frequently have wide fluctuations in serum creatinine (and therefore eGFR) which are not representative of true renal dysfunction. Chronic kidney disease is defined as eGFR  $<60$  mL/min/1.73 m^2 for  $\geq 3$  months [28], with or without kidney damage.

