#### **7.4.2.3 Recovery of eGFR**

Subjects experiencing a decrease in eGFR with resultant decrease in dose should be reassessed for recovery of renal function. If the repeated eGFR is  $>$ 80% of baseline, the dose should be increased by 1 capsule BID and eGFR assessed within 2 weeks.

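### A Cohort 1 subject raised from 23.7 to 39.5 mg BID has no required eGFR or BP check until the next scheduled visit, nominally up to 42 days later

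*Combined protocol and SAP*

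**What the plan says.** Three places in the protocol permit the increase, each conditional on 39.5 mg BID being the Cohort 2 dose. Section 7.1.2.1 says that "subjects still receiving treatment in Cohort 1 may have their dose increased to 39.5 mg BID after Week 8 per Investigator judgement", after discussion with the Medical Monitor. Section 7.4.1 describes the eligible subject as one "who has completed 8 weeks of treatment and shown no meaningful improvement in proteinuria may have their dose increased to 39.5 mg BID". Section 2.1 says the same in substance. None of the three attaches a follow-up measurement.

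Renal function is tied to visits: under section 7.4.2, creatinine and eGFR "will be used for the assessment of renal function at every visit including unscheduled visits". Section 4.1 sets the scheduled visits: "All subjects will return for assessment of efficacy and safety at Weeks 2, 4, 8, 12, 18, and 24". The Schedule of Events puts vital signs and laboratory tests at each of them.

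Two rules link a dose change to a check within 2 weeks:

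- Section 9.2.5 requests a visit "After dose reduction at any time during the study (unscheduled visit within 2 weeks"; its other triggers are a QTcF finding, an eGFR fall already measured, and hypertension that is already symptomatic.
- Section 7.4.2.3 covers recovery after an eGFR-driven reduction: "the dose should be increased by 1 capsule BID and eGFR assessed within 2 weeks".

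The increase to 39.5 mg falls under neither. Section 9.1.6 asks for a PK blood sample when a dose modification is required, but names no eGFR or BP measurement and no time after the change.

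**The concern.** Section 2.1 says of the BP and renal risks that "these risks are dose-related, reversible, and can be managed by dose reduction and temporary interruption". That strategy works only if the problem is measured in time. The eGFR rules in sections 7.4.2.1 and 7.4.2.2 start from a measured value, and the rule in section 7.7 for withholding treatment needs symptoms as well as a high reading. After a two-capsule step to a dose the subject has not taken before, an eGFR fall or an asymptomatic BP rise could go unmanaged for about 6 weeks. Subjects may have entered with an eGFR only just above 45 mL/min/1.73 m² (section 5.3). For a subject raised at Week 18, the first scheduled check is the end-of-treatment visit, so dose adjustment is no longer possible and recovery can only be followed at Weeks 25 and 26.

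What is at stake is timely detection in individual subjects. The point does not say that any efficacy or safety summary would be biased, nor that 39.5 mg is harder on the kidney. Section 1.2.4 reports permanent discontinuation for decreased GFR in 7.9% of lupus nephritis subjects at 23.7 mg BID and 5.7% at 39.5 mg BID.

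**Working it through.** The plan gives no figure for the time from a dose increase to the next check, so there is none to reproduce. The inputs are the visit weeks (section 4.1), the windows in the Schedule of Events (Weeks 4, 8 and 12 ±3 days, Week 18 ±5, Week 24 ±7), and the first dose on Day 2 (section 9.2.2: "Subjects will take their first dose of study medication on Day 2").

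1. **Dose step.** 39.5/23.7 = 1.67, an increase of 67% (3 to 5 capsules BID).
2. **Nominal gap if raised at a visit** = (next week − current week) × 7.
   - Week 8 to 12: 4 × 7 = 28 days
   - Week 12 to 18: 6 × 7 = 42 days
   - Week 18 to 24: 6 × 7 = 42 days
3. **Largest in-window gap** (early visit, then late visit).
   - Week 12 to 18: 42 + 3 + 5 = 50 days
   - Week 18 to 24: 42 + 5 + 7 = 54 days
   - Week 8 to 12: 8 weeks of treatment must be complete. From Day 2, 56 days end on Day 57. The Week 12 visit is Day 85 + 3 = Day 88 at the latest, so 88 − 57 = 31 days.
4. **Increases between visits.** The gap still exceeds 14 days for any increase in the first 42 − 14 = 28 days after the Week 12 or 18 visit, or the first 28 − 14 = 14 days after the Week 8 visit.
5. **Waiting for UPCR.** Central-laboratory turnaround is not stated. If the decision waits an assumed 3 to 7 days for that visit's result, the gaps are 42 − 7 = 35 to 42 − 3 = 39 days, or 28 − 7 = 21 to 28 − 3 = 25 days.
6. **Same step in Cohort 2.** At 39.5 mg the step from 3 to 5 capsules comes at the start of Week 4, Day 22 or 23. The Week 4 visit is Day 29 ±3, that is Day 26 to 32. The gap is 26 − 23 = 3 to 32 − 22 = 10 days.
7. **Who can be affected.** The first 5 or 6 subjects can be raised only after the Week 12 review, so the Week 8 case applies to at most 10 − 6 = 4 or 10 − 5 = 5 later Cohort 1 subjects.

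So the same step is followed by a scheduled check within about 10 days in Cohort 2, and after up to 42 nominal days in Cohort 1.

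**The case against.** The strongest reply is that the increase is already controlled case by case. It needs the Week 12 safety review that selects 39.5 mg, the Investigator's judgement and the Medical Monitor's agreement to discuss it. Unscheduled safety visits are allowed at any time and would include eGFR. A blood draw for PK is due at a dose modification, and if it happens at a visit eGFR would be measured around then. The two 2-week rules follow a tolerability problem, whereas the subject raised here is a non-responder already checked at Weeks 2, 4 and 8. Section 7.4.2.1 even allows re-escalation after an unconfirmed eGFR fall on Medical Monitor discussion alone, with no timed eGFR. Six-week intervals after Week 12 also apply to every Cohort 2 subject. Few subjects will be raised, and the 28- and 42-day figures need an increase on the visit day itself.

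Much of this stands as a limit on size. The two rules are precedents and not identical situations, the numbers are small, and the longest gaps are upper ends. But none of these controls requires a measurement after the increase. The Week 12 review rests on subjects assigned 23.7 mg BID and cannot show how an individual tolerates 39.5 mg. The discussion comes before the step, unscheduled visits are discretionary, and the PK rule fixes neither eGFR, BP nor timing. The restart rule concerns a different situation. The 6-week interval in Cohort 2 comes well after the step and not directly after it.

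**Conclusion.** The concern holds. After a Cohort 1 increase to 39.5 mg BID, the next required eGFR and BP check is the next scheduled visit: nominally 42 days away from Week 12 or 18 (50 and 54 days at the window limits) and 28 days from Week 8 (about 31 at the limit), with shorter gaps for increases between visits. This rests on 39.5 mg being selected and on the subject being still on treatment, without meaningful improvement, and raised by the Investigator; probably only a few subjects meet all of these. It is worth correcting as an inexpensive safety improvement in line with the 2-week interval the protocol uses elsewhere. No analysis or conclusion changes.

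**What to change.** Add one item to the list in section 9.2.5: *after a Cohort 1 dose increase to 39.5 mg BID, an unscheduled visit within 2 weeks with central-laboratory creatinine/eGFR, electrolytes and BP*. State that a scheduled visit falling within those 2 weeks serves the purpose, and cross-refer from sections 7.1.2.1 and 7.4.1. The longest time to a required check falls from a nominal 42 or 28 days to 14. The rules on whether and how the dose is raised stay as they are.

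The cost is one list item and two cross-references in an amendment, and about one extra visit with routine tests for each raised subject. There is no extra visit where a scheduled one already falls within 2 weeks.
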